## 8. TRAINING

#### Training in the use of Digital Pathology

The aim of initial training is to train the pathologist in the use of the digital pathology (DP) system. Training will be provided to pathologists who do not use DP as part of regular practice by the study Pathology Research Fellow and Philips training manager using the Royal College of Pathologists 'Best practice recommendations for implementing digital pathology' January 2018 (26).

Training slide sets will be compiled for each site. Glass slides will be scanned at Coventry and sent back to the home site. Digital slides will be available to view on the Philips Image Management System. Training will include an initial basic skills training to demonstrate how to use the system. This will be followed by providing 5-10 practice samples to each pathologist which they can review and practise in their own time. Finally, a test set of 20 cases will be provided to the pathologist from the Royal College of Pathologists 'Best practice recommendations for implementing digital pathology' guidance and findings will be recorded on the proforma to see how confident they are in analysing digital slides. RCPath approval has been gained for 6 CPD credits for training. The outcomes of the training will be recorded and if needed further training can be provided. Once the training process is complete and sign off has been granted by the Pathology Research Fellow, pathologists will be ready to review study cases.

#### Site initiation

Each site underwent a site initiation where the lead pathologist and their teams participated in an induction session. This was carried out by site initiation visit.

A checklist was completed for all sites to confirm that pre-activation activities were completed. Support is offered by relevant study team members to staff at participating sites to ensure they remain fully aware of study procedures and requirements. Additional support and training is offered to sites where necessary.

## 9. INFORMED CONSENT

The study involves use of previously collected tissue for routine pathology assessment. All samples will be anonymised and returned to the site once all diagnoses have been completed. Therefore, no patient consent is required.

## **10. WITHDRAWALS AND REPLACEMENT**

Case samples may be excluded from the study if they are damaged during their transportation. In this situation, a further slide set will need to be identified as a replacement.

## **11. END OF STUDY**

The completion of the ground truth and analysis of all reports by consensus diagnosis will be considered as end of study.

The study will be stopped prematurely if funding for the study ceases.

The Health Research Authority will be notified in writing within 90 days when the study has been concluded or within 15 days if terminated early.

## **12. STATISTICAL ANALYSIS**

## **12.1** Power and sample size

Three measures will be used to quantify concordance in this study: percentage concordance, Kappa Statistic (KS) and intra class correlation (ICC). In consideration of the appropriate sample size for this study, we assessed the precision of percentage concordance estimates.

Percentage concordance for the routine samples is assumed to be 98.8% (7). The percentage concordance for the difficult samples ranges from 40%-70% (16-25), and so we assume it to be 55%. We assume the percentage concordance for moderate samples to be 75% (a percentage between those for difficult and routine samples). The weighted percentage concordance within our study, with the specified 10% difficult, 10% moderate and 80% routine proportions, is expected to be 90%.

For each of breast, GI and skin, 600 specimens will be included, leading to 4,800 diagnoses (i.e. 600\*4 pathologists\*2 readings). For renal, 200 specimens will be included, leading to 1,600 diagnoses.

Taking into account the expected percentage concordance, we take ICC for routine, moderate and difficult samples to be 0.9, 0.7 and 0.4 respectively. This corresponds to an overall ICC of about 0.8. Hence, the design effect is (1+ICC(observations per specimen-1))=3.4.

Consequently, 2400 paired diagnoses (a pair consists of DP and LM diagnoses of each sample by a pathologist) is equivalent to 705 (2400/3.4) independent observations. With 705 independent observations the margin of error (1.96 x Standard error) is 2.2% so that the precision while analysing breast cancer, skin and GI specimens separately is high. Due to a smaller sample size for renal specimens, the margin of error is 3.1%.

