This study is designed around teams of four pathologists, blind to the original diagnoses, all examining the same series of samples, using both LM and DP. The modality each pathologist views/reports on first will be randomised for each batch of samples, and there will be a minimum of a six-week washout period between LM and DP viewings. Reports will then be scrutinised by a trained Research Fellow independent of the reporting pathologists. Differences detected will be classified by an independent pathologist into clinically important (would alter the clinical management) or clinically unimportant (would not alter the clinical management). The original diagnosis will serve as the reference diagnosis. The ground truth (GT) for each sample is decided on conclusion of the readings, by consensus of the study pathologists, taking into account the reference diagnosis. This allows comparison of each pathologist's performance on LM and DP against the GT. The study will examine 2000 histopathology samples including 600 samples each of breast, gastrointestinal (including 200 cancer screening samples) and skin, and 200 renal samples taken for native or transplant related renal disease. The renal biopsies will include immunofluorescence for detection of immunoglobulin deposits. The population of samples enrolled will be a combination of sequentially selected samples and those from study centres' archives. With the exception of renal, samples will also be enriched with at least 10% moderately difficult and at least 10% difficult samples.

A Health Economic evaluation will involve estimating the core costs and benefits associated with DP, compared with LM. This will involve estimating the impact of switching to DP on throughput, and translating this into the impact on the time to establishing a treatment plan. It will further involve assessing samples of discrepancy to investigate the impact on treatment decisions, and the incremental costs and benefits resulting from this impact. This will be for all discrepancies if feasible, or a purposive sample (selected based on material impact on health and cost outcomes).

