While most previous studies show good LM/DP agreement, (6) (7, 8) (9) some (10) raise concerns over the suitability of DP for diagnosis. Particular concern has been raised about the use of DP for examining samples taken as part of the NHS cancer screening programmes for breast, bowel and cervical cancers.

Our team includes UK leaders in pathology at six NHS teaching hospitals and a large pathology network. We have world leading experience in DP having pioneered its use in routine practice, as well as vast experience of pathology practice and research. The pathologists taking part are a diverse group including highly experienced, relatively junior, early adopters of DP and - a majority - new to DP. The study plan is based on eight viewings of each sample by four pathologists with LM and also with DP, culminating in a consensus ground truth (GT), enabling measurement of agreement within and between readers. Samples enrolled will reflect routine practice. The samples will include cancer screening biopsies and will be enriched for areas of difficulty such as dysplasia (7, 10, 11). State-of-the-art DP equipment designed for diagnosis and holding either CE or FDA approval will be used in this study.

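### Section 12.1 gives the weighted concordance as 90%, but its own inputs yield 92.0%; the margin of error is then 2.0%, not 2.2%, a small error on the cautious side

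*Protocol*

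**What the plan says.** Section 12.1 of the protocol sizes the study on the precision of percentage concordance. It sets an expected value for each difficulty level:

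- Routine samples: 98.8%, taken from a cited validation study.
- Difficult samples: "The percentage concordance for the difficult samples ranges from 40%-70% (16-25), and so we assume it to be 55"%.
- Moderate samples: "We assume the percentage concordance for moderate samples to be 75"%, chosen as lying between the other two.

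It combines them in one sentence: "The weighted percentage concordance within our study, with the specified 10% difficult, 10% moderate and 80% routine proportions, is expected to be 90"%.

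The section then takes ICCs of 0.9, 0.7 and 0.4 for routine, moderate and difficult samples and summarises them as about 0.8 overall. With four paired readings per specimen this gives a design effect of 3.4, which reduces 2400 pairs per specialty to 705 independent observations. The result for breast, GI and skin is: "With 705 independent observations the margin of error (1.96 x Standard error) is 2.2"%.

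**The concern.** The expected concordance is presented as a calculated quantity. All three inputs and all three weights are given, and the result is tied to them: "with the specified 10% difficult, 10% moderate and 80% routine proportions, is expected to be 90"%. A reader who does the multiplication gets a different answer.

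The binomial variance depends on this value, so the discrepancy passes into the margin of error. The 90% and the 2.2% are the only expected concordance and precision that section 12.1 gives for three of the four specialties. If the true error were in the other direction, the study would be less precise than claimed and the number of specimens might need another look. The direction and size therefore have to be worked out before the point is given any weight.

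**Working it through.** **Inputs, all from section 12.1.** Concordance p = 98.8%, 75% and 55%; weights w = 0.80, 0.10 and 0.10; ICC = 0.9, 0.7 and 0.4 (routine, moderate, difficult). Each of breast, GI and skin has 600 specimens read by 4 pathologists, giving 2400 LM/DP pairs.

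**Step 1: reproduce the plan's margin from its own 90%.**
- Design effect = 1 + ICC × (4 − 1) = 1 + 0.8 × 3 = 3.4.
- Effective observations = 2400 / 3.4 = 705.9, stated as 705.
- Margin = 1.96 × √(p(1 − p)/n) = 1.96 × √(0.90 × 0.10 / 705) = 2.21%, stated as 2.2%.

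Everything after the 90% therefore follows correctly from it.

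**Step 2: recompute the weighted concordance.**
- 0.80 × 98.8 + 0.10 × 75 + 0.10 × 55 = 79.04 + 7.50 + 5.50 = 92.04%.

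The stated 90% does not reproduce.

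**Step 3: can 90% be reached from the stated material?**
- Rounding: 92.04% rounds to 92%.
- Low end of the difficult range (40%): 79.04 + 7.50 + 4.00 = 90.54%.
- High end (70%): 79.04 + 7.50 + 7.00 = 93.54%.
- Equal shares of moderate and difficult that would give 90%: (98.8 − 90) / [(98.8 − 75) + (98.8 − 55)] = 8.8 / 67.6 = 13.0% of each, instead of 10%.

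No value in the protocol's range for difficult samples takes the 80/10/10 mix down to 90%.

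**Step 4: the margin at the correct value.**
- 1.96 × √(0.9204 × 0.0796 / 705) = 2.00%.

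**Step 5: does rounding the ICC matter?**
- Weighted ICC = 0.80 × 0.9 + 0.10 × 0.7 + 0.10 × 0.4 = 0.83.
- Design effect = 1 + 0.83 × 3 = 3.49; effective observations = 2400 / 3.49 = 688.
- Margin at 92.04% = 2.02%.

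The corrected margin is 2.0% with either ICC.

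**The case against.** The strongest reply is that nothing turns on the error. The 2.2% follows correctly from 90%, and putting 92.04% in its place makes the study slightly more precise than stated. That stands: neither the sample size nor the judgement of high precision is affected. A related reply is that 90% may be a cautious choice. That is possible, since even the low end of the range for difficult samples gives 90.5%. But the text calls 90% the weighted value at exact proportions and says nothing about caution, so as written it is wrong.

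A reader might infer several stronger points. The protocol does not support them as errors.

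- *That the calculation ignores the difficulty strata.* It does not. They enter as weights for the concordance and again for the ICC. Only the variance is pooled, which is a simple and conservative planning choice.
- *That the margin should be 1.5%.* A stratified variance with 480/60/60 specimens and the stratum ICCs gives 1.54%; with a common design effect of 3.4 it gives 1.70%. The 1.54% is 23% narrower than the corrected 2.00% (1 − 1.54/2.00). It assumes that the stratum sizes are fixed, and it omits clustering by reader with only four readers per specialty. Printing it would overstate the precision.
- *That the pooled figure will move with the mix achieved by more than its own margin.* The Introduction says that "samples will also be enriched with at least 10% moderately difficult and at least 10% difficult samples", and section 4 also treats the shares as minimums, so overshoot is allowed. Section 7.1, however, lists the difficult share as 10% without that qualifier, and no section suggests how large an overshoot might be. A 15/15 mix, for example, would give 0.70 × 98.8 + 0.15 × 75 + 0.15 × 55 = 88.7%, but that mix is hypothetical. Section 12.2 already plans results by difficulty level, and those do not shift with the mix in the way the pooled value does.
- *That section 3 passes off an enriched sample as routine.* It says "Samples enrolled will reflect routine practice", but goes straight on to disclose the screening biopsies and the enrichment.
- *That section 12.2 should name difficulty and specialty as model terms.* Such detail is commonly left to the SAP, which is not at hand, so its absence from the protocol shows nothing.

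**Conclusion.** The point holds as an arithmetic error in two planning figures. On the protocol's own inputs the expected concordance is 92.0%, not 90%, and the margin for each of breast, GI and skin is 2.0%, not 2.2%. The published margin is too wide by about 0.2 percentage points, so the error is conservative and the sample size is not undermined.

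The conclusion rests on the stated stratum concordances, the exact 80/10/10 mix, and the protocol's method of one pooled binomial variance with one design effect. It takes those assumptions as given and does not judge whether they are realistic. It does not cover the renal margin.

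**What to change.** In section 12.1, do one of two things:

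1. Replace 90% with 92.0% and 2.2% with 2.0%; or
2. Keep 90% and 2.2%, and add that the weighted value of the inputs is 92.0% (margin 2.0%) and that the lower concordance was adopted on purpose as a cautious planning value.

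Either is a change to one or two sentences, with no effect on the number of specimens, the data collected or the conduct of the study. The stratified 1.5% should not be substituted.

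As a suggestion only: because sections 2 and 4 set the enrichment shares as minimums, the overall concordance could also be reported standardised to the 80/10/10 mix, next to the difficulty subgroups already planned. Section 7.2.1 has difficulty level recorded at enrolment for Belfast, Nottingham and Lincoln, and section 7.2.2 describes a similar process for Coventry, so no new data should be needed.

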## 7.4 Reporting pathologists

Six NHS histopathology laboratories (Coventry, Belfast, Lincoln, Oxford, Nottingham, Birmingham) will each have specialist pathologists to report on relevant disease areas. In each area, four pathologists will report the same series of samples twice, once each with LM and DP, thereby allowing comparison within and between observers over both platforms.

Centre/disease specialty	GI	Skin	Breast	Renal
Coventry	[name]	[name] [name]		[name]
Belfast	[name] [name]	[name]	[name]	
Lincoln		[name]	[name]	
Nottingham	[name]		[name] [name]	
Oxford				[name] [name]
Birmingham				[name]

Specialist reporting pathologists at each centre by specialty are shown below:
--

The estimated time to make these readings based on current work-diary exercise data is one 4 hour session per week over 24 months.

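### Section 12.1 pools the stratum ICCs by specimen share and uses 90% concordance; its own inputs give 92.04%, an overall ICC of about 0.71 and a margin of about 1.9% rather than 2.2%

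*Protocol*

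**What the plan says.** Section 12.1 of the Protocol bases the sample size on the precision of percentage concordance. It assumes concordance by difficulty: "Percentage concordance for the routine samples is assumed to be 98.8" per cent, "We assume the percentage concordance for moderate samples to be 75" per cent, and 55% for difficult samples. It then says that the weighted concordance, "with the specified 10% difficult, 10% moderate and 80% routine proportions, is expected to be 90" per cent. For clustering of the four readings within a specimen, "we take ICC for routine, moderate and difficult samples to be 0.9, 0.7 and 0.4 respectively", followed by "This corresponds to an overall ICC of about 0.8". It continues: "Hence, the design effect is (1+ICC(observations per specimen-1))=3.4". The 2400 DP/LM pairs per specialty are then taken as worth 705 (the text: "is equivalent to 705 (2400/3.4) independent observations"), which leads to a 2.2% margin of error for each of breast, GI and skin.

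The four observations per specimen come from Section 7.4: "In each area, four pathologists will report the same series of samples twice, once each with LM and DP". Each pathologist therefore contributes one DP/LM pair per specimen.

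**The concern.** The section presents the overall ICC as what the three stratum ICCs amount to when combined. The only simple combination that gives about 0.8 is the mean weighted by number of specimens. For a yes/no outcome an ICC is the between-specimen variance divided by the total variance. Strata must therefore be combined on the variance scale, and the spread of the stratum concordances counts as between-specimen variance.

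Routine samples supply 0.72 of the 0.83 in the share-weighted mean. At 98.8% concordance they hold only about 13% of the total outcome variance (0.0095 of 0.0733).

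The weighted concordance of 90% also differs from what the stated proportions give. Section 12.1 contains no hypothesis test and no power figure, so the margin is its only quantitative support for 600 specimens per specialty. It should follow from the assumptions printed beside it.

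**Working it through.** **Inputs (Section 12.1).** Weights w = 0.8, 0.1, 0.1; concordances p = 0.988, 0.75, 0.55; ICCs = 0.9, 0.7, 0.4; 2400 pairs; four pairs per specimen (Section 7.4).

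**1. The plan's own figures.**
- Share-weighted ICC = 0.8×0.9 + 0.1×0.7 + 0.1×0.4 = 0.83, stated as about 0.8.
- Design effect = 1 + 0.8×3 = 3.4.
- Effective n = 2400/3.4 = 705.9.
- Margin at 90% = 1.96×√(0.90×0.10/705.9) = 2.21%.

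Every step reproduces. With 0.83 unrounded, the design effect is 3.49, the effective n is 688 and the margin is 2.24%, which still rounds to 2.2%.

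**2. Weighted concordance.** 0.8×98.8 + 0.1×75 + 0.1×55 = 79.04 + 7.5 + 5.5 = 92.04%.

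**3. Pooled ICC of the binary outcome.** The stratum variances p(1−p) are 0.01186, 0.1875 and 0.2475.
- Within-stratum covariance, Σ w×ICC×p(1−p) = 0.00854 + 0.01313 + 0.00990 = 0.0316.
- Between-stratum variance, Σ w×(p − 0.9204)² = 0.00366 + 0.00290 + 0.01372 = 0.0203.
- Total variance = 0.9204×0.0796 = 0.0733.
- Overall ICC = (0.0316 + 0.0203)/0.0733 = 0.71 (0.708 from unrounded terms).

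**4. Margin from the pooled ICC.**
- Design effect = 1 + 3×0.708 = 3.12.
- Effective n = 2400/3.12 = about 769.
- Margin = 1.96×√(0.0733/769) = 1.91%.

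**5. Which change does what.**

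| ICC | Concordance | Margin |
|---|---|---|
| 0.80 | 90% | 2.21% |
| 0.71 | 90% | 2.12% |
| 0.80 | 92.04% | 2.00% |
| 0.71 | 92.04% | 1.91% |

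The ICC alone moves the margin by about 0.1 percentage point. The concordance accounts for about 0.2.

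**6. Mix held fixed at 80/10/10.** No overall ICC is needed. The variance is Σ w×p(1−p)×(1 + 3×ICC)/2400.
- Sum = 0.8×0.01186×3.7 + 0.1×0.1875×3.1 + 0.1×0.2475×2.2 = 0.0351 + 0.0581 + 0.0545 = 0.1477.
- Margin = 1.96×√(0.1477/2400) = 1.54%.

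Steps 4 and 6 agree with each other. Their variances differ by the between-stratum variance over 600 specimens (0.0203/600 = 0.000034). Adding that to 0.1477/2400 = 0.0000615 gives 0.0000953, and 1.96×√0.0000953 = 1.91%.

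**The case against.** The strongest case for leaving the text alone is that its chain is declared, reproducible and on the safe side. Three parts of that case stand.

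- A reader might infer that 0.8 is an arithmetic slip for 0.83. It is not: 0.83 is fairly described as about 0.8, and the margin stays at 2.2% either way. At 90% concordance, any overall ICC from about 0.74 to 0.84 gives 2.2%.
- Most of the move from 2.2% to 1.9% comes from 92.04% against 90%, not from the ICC. The two parts should be reported separately.
- A reader might take 1.5% as the margin the design really has. The Protocol does not support that as the main figure. Section 12.2 plans logistic regression with a random effect for repeated results per sample, names no adjustment for difficulty, and leaves difficulty to subgroup exploration. Section 2 sets the enriched shares as minimums, and Section 4 has the pilot test whether they are feasible. The 1.5% is conditional on a fixed mix.

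It can also be said that refining the pooling of round assumptions adds little, that conclusions about precision do not change, and that the final intervals will come from the data. That argues for low importance. It does not make a specimen-share mean the pooled ICC of a binary outcome. In general that mean is right only when the strata share the same concordance, and here they run from 55% to 98.8%.

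**Conclusion.** The point holds as a minor inconsistency. On Section 12.1's own assumptions, the overall ICC is about 0.71 and the weighted concordance 92.04%, so the margin per specialty for breast, GI and skin is about 1.9% (about 1.5% with the mix fixed). The stated 2.2% is about 16% wider than the first (2.21/1.91) and about 44% wider than the second (2.21/1.54).

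The error is conservative. A reader might infer that the sample size is inadequate; every corrected margin is narrower than the stated one, so the documents do not support that. The opposite inference, that fewer specimens would do, is not supported either. None of these figures includes variation between readers, and with only four pathologists per specialty that could widen the interval by an amount the Protocol gives no basis to estimate.

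The result rests on the assumed stratum concordances and ICCs being taken at face value, on an 80/10/10 mix, and on concordance treated as a yes/no outcome with four pairs per specimen. The renal margin is not part of this point.

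**What to change.** Restate Section 12.1 with a weighted concordance of 92%, an overall ICC of 0.71, a design effect of 3.1, an effective sample of about 769 and a margin of 1.9% for each of breast, GI and skin. Add one line showing how the ICC is formed from the stratum variances and means. Optionally give 1.5% as the margin when the 80/10/10 mix is held fixed, labelled as such. State that neither figure includes variation between the four readers and that neither should be used to reduce the sample size. If the sponsor prefers to keep 2.2% as a cautious planning value, the text should say that 0.8 and 90% are deliberate conservative simplifications.

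The cost is a change of wording in one section, with no new data and no effect on enrolment or reading.

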## 7. SAMPLE PATHWAY

## 7.1 Sample selection criteria

Histopathology samples from five participating NHS trusts will be selected. All samples are collected for the purpose of routine histopathology reporting and only entered into the study on completion of their clinical review at the respective NHS participating site.

There are four sub-specialty areas that are included in the study: breast, gastrointestinal (GI), skin and renal. The sample selection process will be devised to include cancer screening biopsies and will be enriched (20%) for areas of difficulty, with the exception of renal samples where all are considered difficult cases:

- Breast (Belfast, Coventry, Lincoln & Nottingham): A total of 600 samples including at least 200 cancer screening biopsies enriched with:
  - o At least 10% resected tumours (moderately difficult)
  - 10% difficult samples: low grade ductal carcinoma in situ, atypical hyperplasia, screening category B3 and B4, lesions with calcium oxalate (Weddellite calcification), sclerosing and papillary lesions, and micrometastases
- GI (Coventry, Belfast & Nottingham): A total of 600 samples including at least 200 cancer screening biopsies enriched with:
  - At least 10% resected tumours (moderately difficult)
  - 10% difficult: oesophageal dysplasia, polyp cancers, inflammatory bowel disease, minimal change colitis, graft versus host disease, giardiasis, cytomegalovirus, H. pylori and herpes virus infection
- Skin (Coventry, Belfast & Lincoln): A total of 600 samples enriched with:
  - o At least 10% non-basal cell carcinoma cancer resections (moderately difficult)
  - 10% difficult: sentinel nodes, dysplastic naevi, spitz naevi, lentigo maligna, early and desmoplastic melanoma, herpes virus infection, leischmaniasis, leprosy, amyloid, angioscaroma, and Kaposis sarcoma
- Renal (Oxford only): A total of 200 sequential native biopsies for glomerular, tubulointerstitial and vascular disease and transplant biopsies for graft rejection. No enrichment is planned in the renal biopsy group as all of these biopsies are difficult to report.

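### The renal margin of error of 3.1% in section 12.1 does not follow from the smaller sample size, and no consistent pairing of the protocol's assumptions gives it; they give 3.8% or 5.1%

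*Protocol*

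**What the plan says.** Section 12.1 of the protocol bases the sample size on the precision of percentage concordance. The unit is the pair: "a pair consists of DP and LM diagnoses of each sample by a pathologist". For breast, GI and skin there are 2400 pairs per specialty. An overall ICC of about 0.8 gives a design effect of 3.4 and 705 independent observations, and "the margin of error (1.96 x Standard error) is 2.2" per cent. The concordance behind that figure is the weighted value which, "with the specified 10% difficult, 10% moderate and 80% routine proportions, is expected to be 90" per cent.

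For renal the section gives the count, "For renal, 200 specimens will be included, leading to 1,600 diagnoses", and then the result: "Due to a smaller sample size for renal specimens, the margin of error is 3.1" per cent. It prints no concordance, ICC or design effect for renal.

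Two other statements bear on which inputs apply. Section 7.1 says "No enrichment is planned in the renal biopsy group as all of these biopsies are difficult to report". Section 12.1 says "The percentage concordance for the difficult samples ranges from 40%-70% (16-25), and so we assume it to be 55" per cent, and takes the ICC for difficult samples as 0.4.

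**The concern.** The sentence offers the smaller sample as the only reason why 3.1% differs from 2.2%. Renal has one third of the specimens, so with everything else fixed the margin should grow by √3 = 1.73, to about 3.8%. The stated figure is smaller than that, so some other input must have changed without being named.

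Which input changed matters because the 90% concordance and the ICC of 0.8 both belong to a mix of routine, moderate and difficult samples, and section 7.1 keeps renal out of that mix. Renal is analysed separately (section 12.2, subgroup analyses) and has its own planned paper on whether digital pathology can replace light microscopy for renal biopsies (section 19.2). The 3.1% is the only statement of precision that the protocol gives for its 200 renal samples.

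**Working it through.** **Method (section 12.1).** Margin = 1.96 × √(p(1 − p)/n_eff), where n_eff = pairs / (1 + ICC × (m − 1)) and m is the number of observations per specimen. Section 7.4 gives m = 4: "In each area, four pathologists will report the same series of samples twice, once each with LM and DP".

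**Inputs.**
- Renal pairs: 200 × 4 = 800 (1,600 diagnoses / 2).
- Mixed samples: p = 0.90, ICC 0.8 (section 12.1).
- Difficult samples: p = 0.55, cited range 0.40 to 0.70, ICC 0.4 (section 12.1).

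**Step 1: reproduce the main figure.** Design effect 1 + 0.8 × 3 = 3.4. n_eff = 2400/3.4 = 705.9. Margin = 1.96 × √(0.90 × 0.10/705.9) = 2.21%. This agrees with the stated 2.2%, so the method and inputs are read correctly.

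**Step 2: change only the sample size.** n_eff = 800/3.4 = 235.3. Margin = 1.96 × √(0.90 × 0.10/235.3) = 3.83%. The unrounded weighted inputs do not give 3.1% either:
- p = 0.8 × 0.988 + 0.1 × 0.75 + 0.1 × 0.55 = 0.9204
- ICC = 0.8 × 0.9 + 0.1 × 0.7 + 0.1 × 0.4 = 0.83
- design effect 1 + 0.83 × 3 = 3.49, n_eff = 800/3.49 = 229.2
- margin = 1.96 × √(0.9204 × 0.0796/229.2) = 3.50%

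**Step 3: use the difficult-sample inputs throughout.** Design effect 1 + 0.4 × 3 = 2.2. n_eff = 800/2.2 = 363.6.

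| Concordance | Margin |
|---|---|
| 0.40 | 5.04% |
| 0.50 (maximum) | 5.14% |
| 0.55 (assumed) | 5.11% |
| 0.70 | 4.71% |

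**Step 4: look for the source of 3.1%.** Pairing p = 0.90 with ICC 0.4 gives 1.96 × √(0.90 × 0.10/363.6) = 3.08%, which rounds to 3.1%. Working backwards, 3.1% at design effect 2.2 implies p = 0.899. A search covered concordances from 0.40 to 0.988, ICCs from 0 to 0.9, 4 or 8 observations per specimen, and totals of 200, 800 or 1600. It found one other combination that rounds to 3.1%: p = 0.75, ICC 0.4 and 1600 observations (3.15%). That one joins the moderate-sample concordance to the difficult-sample ICC and counts single diagnoses, contrary to the section's definition of a pair.

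**Step 5: size.** 3.83/3.1 = 1.24 and 5.11/3.1 = 1.65.

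**The case against.** The strongest objection is to 5.1% as the replacement. Section 12.1 prints no renal concordance and no renal ICC, so the inputs behind 3.1% are inferred. Section 7.1 calls renal biopsies difficult in order to explain why they are not enriched, not to assign them a concordance. The 40% to 70% range is cited to references 16 to 25. By their titles these concern breast and oesophageal pathology and a neoadjuvant chemotherapy trial; none is renal. Several describe agreement between observers, whereas the primary outcome in section 6 is each pathologist's own agreement across the two modalities. At ICC 0.4, 5.1% is also close to the largest margin possible (5.14%). All of this stands, and it makes 5.1% conditional on applying the difficult-sample assumptions to renal. It does not rescue 3.1%, because the step that changes only the sample size needs no renal-specific assumption and already gives 3.8%.

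A second objection is that little hangs on the figure. Section 12.1 sets no hypothesis test, target width or renal threshold, and the primary analysis pools the specialties. The reported renal precision will come from the observed data through the model in section 12.2. This also stands, and it limits the consequence to a wrong planning figure.

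A reader might infer more: that 5.1% is the true renal interval, that the more favourable inputs were chosen on purpose, that the funder or the steering committee relied on 3.1%, or that 200 renal samples are too few. The documents support none of these. The actual width depends on the concordance observed. The protocol does not show how the figure was produced. No decision is tied to it, and no required renal precision is stated against which 200 samples could fall short.

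**Conclusion.** The renal figure is wrong as written. The reason given leads to 3.8%, and the difficult-sample assumptions that fit section 7.1 lead to 5.1% (4.7% to 5.1% over the cited range). The stated 3.1% appears to combine the concordance of one scenario with the ICC of the other. That explanation is a strong inference and not a documented fact.

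The expected margin is about 1.2 to 1.65 times the stated one. The 3.8% end assumes that renal behaves like the mixed series. The 5.1% end assumes that renal behaves like the protocol's difficult class. Both take the design-effect formula and four readers per specimen as given. If the sponsor expects renal concordance near 90% although all cases are difficult, that departs from the 55% assumed for difficult samples and needs its own justification.

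**What to change.** Amend the renal sentence in section 12.1 in one of two ways:
- If renal samples are treated as difficult, as section 7.1 says, give the margin as about 5.1% (55% concordance, ICC 0.4, design effect 2.2, about 364 effective observations), with 4.7% to 5.1% over the 40% to 70% range.
- If the 90% and 0.8 assumptions are intended for renal, give 3.8% (design effect 3.4, about 235 effective observations) and say why they apply to a group that section 7.1 classes as difficult throughout.

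In either case, print the inputs beside the figure and drop the attribution to sample size alone unless the second option is taken. The cost is one or two sentences and a less favourable planning figure. Enrolment, reading, sample number and analysis are unaffected.
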